2.5.2.3 Immune response

Some members of Ephs and Ephrins are also expressed in the lymphoid organs, and their physiological role in immune responses is still being elucidated.⁵⁶ T cells express EphBs and EphrinBs, both of which can provide co-inhibitory or co-stimulatory signals for T-cell proliferation.⁵⁷ Bidirectional signals via Eph receptors and Ephrins have been recognized as major forms of contact-dependent cell communications. EphrinB1 and EphrinB2 increased CD3-mediated murine T-cell proliferation. However, higher concentrations of EphrinB1 and EphrinB2 suppressed proliferation, a mechanism thought to be by phosphorylating EphB receptors.⁵⁸ Similarly, EphrinB2 knockdown expression in human mesenchymal stem cells (MSC) reduced MSC's ability to inhibit T-cell proliferation.⁵⁹ Therefore, there is evidence that EphB-EphrinB interactions play an important role in mediating activation and inhibition of activated T cells, which may be important for tumor suppression of, and immune response to HHV-8, as well as HIV in this population of patients.

sEphB4-HSA's effect on the immune response at the level of the tumor has not been well defined. However, it appears that sEphB4-HSA alters T-cell function. Preclinical studies show that sEphB4 can increase the migration of T cells into the tumor beds, possibly reinstating and activating T cell function. We hypothesize that the disruption of the EphrinB2-EphB4 interaction will activate T-cells and restore previously blocked T-cell function. This hypothesis will be examined with peripheral blood and

biopsy samples. Peripheral blood samples will be used for flow cytometric analysis, cytokine measurements, and *in vitro* studies. See [Appendices I and III](#) for full details of the blood sample collection times. Participants will have two tumor biopsies obtained before initiation of the study, and two biopsies obtained after one cycle of treatment. See [Appendices I and III](#) for full details of the biopsy collection times. The peripheral blood will be shipped to [name] directly at room temperature.⁶⁰ See [Appendix IX](#) for shipping details. The tumor samples will be stored at the AMC Biorepository and then shipped to each respective center for specific correlative studies to be performed. See [Appendix VIII](#) shipping details. Biopsy samples will be used to perform cytokine assays and evaluate for tumor regression and immune infiltration. Immune studies will be performed as follows pending funding.

Peripheral blood

To measure the potential effects of sEphB4 on immune cell activity, blood samples will be examined using standard 10-color flow cytometry with Ki-67 as a marker of proliferation and standard markers for T (CD3, CD4, CD8, CD25, CD69, CCR5, CCR7, FOXP3), B (CD20), NK (CD56, CD16), NK-T (Va24, CD56, CD3, CD69), monocytes (CD14, HLA-DR, CD64), and neutrophils (FSC, SSC, CD15, CD16). Blood samples will be obtained within 14 days prior to Cycle 1, Day 1 of study drug (Baseline and Day 1 can be the same day), Day 15 of Cycle 1, and Day 1 of Cycles 2, 4, and 6 before study treatment dosing. Mononuclear cells from the blood will be Ficoll-purified and frozen for future functional studies if needed. These may include Enzyme-Linked Immunosorbent Spot (ELISPOT) or cytokine secretion assays using HHV-8 peptides as stimuli. Peripheral blood will be shipped overnight to [name] at George Washington University Medical Center. Flow cytometry will be performed by [name] at the George Washington University Medical Center.

Biopsy

To examine cells in the tissue, IHC will be used to detect cells expressing CD45, CD3, CD20, CD68, and CD163 as initial queries into the types of cells that may be preferentially recruited to the tumor site by sEphB4 treatments. Participants will have biopsies performed within 14 days prior to Cycle 1, Day 1 of study drug (Baseline and Day 1 can be the same day), as well as after one cycle of treatment (can be any time after Cycle 1, Day 15 dosing and before treatment on Cycle 2, Day 1). Immunohistochemistry will be performed at the AMC Core Pathology laboratories by [name].

2.5.2.4 Apoptosis and proliferation

HHV-8 infection reprograms cellular gene expression upregulating proteins important in proliferation and apoptosis. These pathways regulate cell functions which include cell division, cellular stress response and cell death. We hypothesize sEphB4-HSA will alter and modulate various cellular

pathways important in proliferation and apoptosis. We will obtain the following immunohistochemistry staining on the biopsy samples. Participants will have two tumor biopsies obtained within 14 days prior to Cycle 1, Day 1 of study drug (Baseline and Day 1 can be the same day), as well as after one cycle of treatment (can be any time after Cycle 1, Day 15 dosing and before treatment on Cycle 2, Day 1). The tumor samples will be stored at the AMC Repository and then shipped to each respective center for specific correlative studies to be performed. The following correlative studies will be investigated on the biopsy samples:

LANA-1

LANA-1, latency-associated nuclear antigen, is a HHV-8 associated latent protein. LANA-1 is associated with cellular chromatin and stays on the chromosomes during cell division.⁶¹ It is one of the few proteins consistently shown to be expressed by in latent KS, and likely mediates the episomal replication of the HHV-8 genome.^{62,63} It has been showed to be expressed in KS lesions, but the LANA-1 levels are noted to increase throughout tumor progression.⁶⁴ Immunohistochemistry will be performed at the AMC Core Pathology laboratories by [name].

K8.1

The K8.1 glycoprotein is a structural component of the KSHV particle and is thought to facilitate virus entry into the cell. It is a lytic viral antigen and rarely expressed in KS but may be found in a small subset of cases where lytic replication may contribute to KS pathogenesis. In these cases, it has been showed to be predominately expressed in infected KS cells and within virion envelopes. Immunohistochemistry will be performed at the AMC Core Pathology laboratories by [name].

TUNEL

TUNEL detects DNA fragmentation by labeling the terminal end of nucleic acids. It is useful for identifying apoptosis. It has been used to confirm apoptosis in cells infected with HHV-8.⁶⁵ Immunohistochemistry will be performed by [name] at USC Norris Hospital.

CD31

CD31 is also known as platelet endothelial cell adhesion molecule (PECAM-1). CD31 plays a key role in removing aged neutrophils from the body. It is found on platelets, monocytes, neutrophils, some T-cells, and a large portion of endothelial cell intercellular junctions. It is a measure of angiogenesis. CD31 is highly expressed in Kaposi sarcoma and used routinely for the diagnosis of Kaposi sarcoma.⁶⁶ Immunohistochemistry will be performed by [name] at USC Norris Hospital.

2.5.2.5 HIV plasma viral loads and T-cell counts in participants with HIV

HIV plasma viral loads and CD4 and CD8 counts will be ordered routinely by each institution at regular intervals of 3 months. Labs will be drawn

before treatment, and on Day 1 of Cycles 4, 7, 10, and at treatment discontinuation. See [Section 8.0](#) and [Appendix I](#) for details of the collection times. Peripheral blood will be drawn; and viral loads and T-cell counts will be performed at the AMC site in which the participant is being treated.

2.5.2.6 Archive PBMCs, plasma, and tumor biopsies

Blood for PBMCs and plasma, and tissue samples will be collected and archived to be used in conjunction with samples collected from subsequent trials of sEphB4-HSA in KS for future studies including identification of biomarkers predictive of response. One of two tumor biopsies obtained before initiation of the study drug, and one of two biopsies obtained after one cycle of study drug will be saved for future studies. These biopsy specimens will be collected in RNAlater. Biopsies will be stored at the AMC Biorepository. Biopsy for KSHV and targeted endothelium gene transcription will be performed by [name] and the AMC Core Genomics Core labs at the University of North Carolina, Chapel Hill. Pending funding, RNA sequencing via NextGen sequencing will be performed by [name] at the Moores UCSD Cancer Center Genomics and Bioinformatics Shared Resource.

2.6 Quality of Life Measure

The Functional Assessment of HIV infection (FAHI) instrument was adapted from the Functional Assessment of Cancer Therapy – General (FACT-G) questionnaire and found to have acceptable psychometric properties in HIV-infected persons.⁶⁷ The instrument detected changes in the health status of patients that were not detected through conventional efficacy measures. Individual items in the FAHI are scored into the following sub-scales: physical well-being, emotional well-being, functional well-being, social well-being, and cognitive functioning.

In this study, the FAHI plus 3 KS-specific questions will be used to evaluate health-related QOL measures. The KS-specific questions relate to pain, edema or swelling, and physical appearance.

The FAHI + KS instrument has previously been used in the AMC009/ECOG E1D96 study that randomized AIDS-KS participants to receive paclitaxel or liposomal doxorubicin. The treatment arms were combined for the QOL analysis which demonstrated improvements with treatment in cognitive functioning, social well-being, pain and swelling.¹⁸

Like previous AMC studies, each participant will serve as his/her baseline; this will account for variable baseline assessments. While the FAHI+KS questionnaire has not been validated in a large cohort of KS participants, and will not be in this phase II trial, as an exploratory study, the utilization of the same QOL instrument would facilitate comparisons between previous AMC studies. In addition, QOL assessments would provide meaningful education and empowerment for the patient, as well as allow us to examine and describe whether QOL adds to our understanding of sEphB4-HSA's clinical use. All participants, HIV and non-HIV positive, will be assessed via the FAHI+KS questionnaire. Non-HIV KS is typically cutaneous in nature and also associated with the virus KSHV. Patients with non-HIV KS are similarly concerned about appearance, and about spreading the disease

and KSHV virus; these issues are captured by the FAHI+KS questionnaire. sEphB4-HSA is a novel drug, and as we try to move into an era which evaluates alternative treatments beyond chemotherapy drugs, patients may be able to influence the delivery of clinical trials by converting their experience into constructive and productive hypotheses for subsequent trials and future clinical recommendations.

3.0 PARTICIPANT SELECTION

A rostered AMC investigator (Cancer Therapy Evaluation Program [CTEP]-registered physician investigator) must document that each protocol participant meets all stated eligibility criteria. Participating sites must have documentation that each eligibility requirement is satisfied prior to participant enrollment. In compliance with CTEP policy, no exceptions to eligibility criteria will be granted under any circumstance.

NOTE: Institutions may use this section of the protocol as an eligibility checklist for source documentation if it has been reviewed, signed, and dated before registration/randomization by the study investigator. If used as source documentation, this checklist must be printed, the investigator must check each item to document their assessment that the participant meets each eligibility criterion, and the completed checklist must be maintained in the participant's chart.

Participant ID Number: 096 - _____ - _____

Patient's Initials (F, M [optional], L): _____

NOTE: All questions regarding eligibility should be directed to the study chair.

3.1 Eligibility Criteria

- _____ 3.1.1 Participants may be treatment naïve, refractory to, or intolerant of one or more prior therapies, or treated with prior systemic treatment including but not limited to liposomal doxorubicin.
- _____ 3.1.2 Participants must have biopsy-proven KS involving skin, with or without visceral involvement.
- _____ 3.1.3 If HIV-positive, any CD4 count will be allowed on study.
- _____ 3.1.4 Age \geq 18 years.
- _____ 3.1.5 Eastern Cooperative Oncology Group (ECOG) performance status \leq 2 or Karnofsky performance score (KPS) \geq 50% ([Appendix IV](#)).
- _____ 3.1.6 Life expectancy of greater than 3 months.
- _____ 3.1.7 Participants must have normal organ and marrow function as defined below within 21 days of enrollment:

Absolute neutrophil count (ANC)	\geq 1,500/mcL*
Platelets	\geq 100,000/mcL
Total bilirubin	\leq 1.5 X upper limit of normal (ULN)
aspartate aminotransferase (AST) or serum glutamic-oxaloacetic transaminase (SGOT) / alanine aminotransferase (ALT) or serum glutamic pyruvic	\leq 2.5 X ULN

transaminase (SGPT)	
Creatinine within normal institutional limit for the reference lab OR creatinine clearance	≥ 60 mL/min/1.73 m ² as calculated by Cockcroft-Gault formula for participants with creatinine levels above institutional normal

*Participants may be receiving growth factor support to meet these criteria

- _____ 3.1.8 Participants must have cutaneous lesion(s) amenable to four (4) 5-mm tumor biopsies during the study (either 4 separate lesions measuring ≥ 5 mm each OR 2 separate lesions measuring ≥ 10 mm each) and at least five additional lesions measurable for assessment with no improvement over the past month.
- _____ 3.1.9 Females of childbearing potential (FCBP)[†] must have a negative serum or urine pregnancy test with a sensitivity of at least 25 mIU/mL within 14 days prior to enrollment and again within 24 hours prior to starting Cycle 1 of sEphB4-HSA. Further, they must either commit to continued abstinence from heterosexual intercourse or begin TWO acceptable methods of birth control: one highly effective method and one additional effective method AT THE SAME TIME during receipt of sEphB4-HSA, and 12 weeks after discontinuation of sEphB4-HSA. FCBP must also agree to ongoing pregnancy testing. Men must agree to use a latex condom during sexual contact with a FCBP even if they have had a successful vasectomy. See [Appendix XI](#): Risks of Fetal Exposure, Pregnancy Testing Guidelines and Acceptable Birth Control Methods.
- [†] A female of childbearing potential is a sexually mature woman who: 1) has not undergone a hysterectomy or bilateral oophorectomy; or 2) has not been naturally postmenopausal for at least 24 consecutive months (i.e., has had menses at any time in the preceding 24 consecutive months).
- _____ 3.1.10 Documentation of HIV status. If participant is HIV positive, HIV-1 infection, as documented by any federally approved, licensed HIV rapid test performed in conjunction with screening (or ELISA test kit, and confirmed by Western blot or other approved test, or HIV rapid multispot antibody differentiation assay). Alternatively, this documentation may include a record demonstrating that another physician has documented the participant's HIV status based on either: 1) approved diagnostic tests, or 2) the referring physician's written record that HIV infection was documented, with supporting information on the participant's relevant medical history and/or current management of HIV infection.
- If the participant is HIV-negative, documentation of a negative result for any federally approved, licensed HIV rapid test within 4 weeks prior to study enrollment will suffice. If the initial rapid test is positive, further approved confirmatory test results must be present to document the subject's HIV status.
- _____ 3.1.11 If participant is HIV positive, participant must be on a stable antiretroviral regimen for at least 12 weeks prior to study enrollment.
- _____ 3.1.12 There should be no evidence for improvement in KS in the 3 months prior to study enrollment, unless there is evidence for progression of KS in the 4 weeks

immediately prior to study enrollment.

- ____ 3.1.13 Participants must, in the opinion of the investigator, be capable of complying with the protocol.

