- 8.1.6 Laboratory studies must be obtained within 21 days (unless otherwise noted) prior to enrollment and will include the following:
- Complete blood count (CBC) with differential.
 - Serum chemistries, liver enzymes (AST (SGOT), ALT (SGPT), alkaline phosphatase), BUN, creatinine, electrolytes (sodium, potassium, chloride, bicarbonate, calcium, phosphorus, glucose) albumin, total protein, bilirubin (direct and indirect).
 - If HIV positive, T-lymphocyte subsets (CD4 and CD8) counts and percentages within 28 days prior to study enrollment.
 - If HIV positive, HIV-1 plasma RNA within 28 days prior to study enrollment.
 - Females of childbearing potential (FCBP)[†] must have a negative serum or urine pregnancy test with a sensitivity of at least 25 mIU/mL within 14 days prior to study enrollment and again within 24 hours of starting sEphB4-HSA, and must either commit to continued abstinence from heterosexual intercourse or begin TWO acceptable methods of birth control, one highly effective method and one additional effective method AT THE SAME TIME. FCBP must also agree to ongoing pregnancy testing. Men must agree to use a latex condom during sexual contact with a FCBP even if they have had a successful vasectomy. See [Appendix XI](#): Risks of Fetal Exposure, Pregnancy Testing Guidelines and Acceptable Birth Control Methods.
- [†] A female of childbearing potential is a sexually mature woman who: 1) has not undergone a hysterectomy or bilateral oophorectomy; or 2) has not been naturally postmenopausal for at least 24 consecutive months (i.e., has had menses at any time in the preceding 24 consecutive months).
- Urinalysis
- 8.1.7 Biologic endpoints: peripheral blood for biologic endpoints as described in [Appendices I](#) and [III](#) will be collected at baseline, including blood for research purposes. The samples include blood for HHV-8 viral loads, immune studies, and archived research purposes. Screening and Day 1 of Cycle 1 blood samples can be

on the same day as long as the screening was done within 14 days of Day 1 of the study drug.

- 8.1.8 Complete physical exam including the following: vital signs (temperature, pulse, BP, and respiratory rate), height, weight, tumor assessment, and ECOG or KPS performance status. All BP measurements will be obtained after the participant has been sitting in a sitting or supine position for 5 minutes or longer.

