- 8.2.1.15 Two 5-mm punch biopsy specimens (one stored in RNAlater and the other formalin fixed) to be collected from a non-indicator lesion(s) on Day 1 of Cycle 1 prior to treatment. Biopsies may be obtained within 14 days prior to Day 1 of Cycle 1. Two biopsies can be performed on two separate non-indicator lesions measuring > 5 mm OR performed on one non-indicator lesion measuring > 10 mm in size. Screening and Day 1 samples can be on the same day. Then, two 5-mm punch biopsy specimens (one stored in RNAlater and the other formalin fixed) will be collected from a non-indicator lesion (s) on Day 15 of Cycle 1 after completion of one cycle

(two doses) of treatment (biopsies may be collected up until Day 1 of Cycle 2). Two biopsies can be performed on two separate non-indicator lesions measuring > 5 mm OR performed on one non-indicator lesion measuring > 10 mm in size.

8.2.1.16 Females of Childbearing Potential (FCBP) with regular, irregular or no menstruation must have a pregnancy test before study enrollment and on Day 1 (see [Appendix XI](#): Risks of Fetal Exposure, Pregnancy Testing Guidelines and Acceptable Birth Control Methods); the test must be done within 24 hours before starting the study drug. All participants must be counseled about pregnancy precautions, risks of fetal exposure, and other risks.

8.2.1.17 Functional assessment of HIV Infection (FAHI) + Kaposi sarcoma (KS) QOL questionnaire ([Appendix XII](#)). Those who have HIV-negative KS will not have the HIV portion scored. Screening and Day 1 questionnaire may be the same if the screening was done within 14 days of starting the study drug.

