APPENDIX I: SCHEDULE OF EVALUATIONS

Baseline evaluations are to be conducted within 21 days prior to start of protocol therapy, unless otherwise specified. Scans and x-rays must be done ≤ 28 days prior to the start of therapy. In the event that the participant's condition is deteriorating, laboratory evaluations should be repeated within 48 hours prior to initiation of the next cycle of therapy. Please note, hypertension is a known and expected side effect of this drug. Please see [Section 5.4](#) for special considerations for participants with cardiac risk factors (history of hyperlipidemia, smoking, diabetes, treatment for hypertension, African American ethnicity) and specific instructions for participants who develop \geq grade 2 hypertension while on treatment.

	Eligibility	Screening/ Baseline	Cycle 1 Day 1	Cycle 1 Day 15	Cycles 2 – 12				Treatment Discont.	Post Treatment Eval.	Follow Up Visits
					Day 1		Day 15				
Informed Consent	X ^a										
Documentation of HIV status		X ^a									
KS Biopsy (Diagnostic)	X ^a										
Complete Medical History		X									
Complete Physical Exam ^s , Complete Review of Signs and Symptoms, and Review of AIDS- defining events		X	X ^g	X ^h	X ^h		X ^h		X	X	X
ECOG or KPS Performance Status	X	X	X ^g	X ^h	X ^h				X	X	
Toxicity Assessment		X ^{bb} (hyper- tension only)	X ^{bb} (hyper- tension only)	X ^{h, bb}	X ^{h, bb}				X	X	
EKG		X ^v									
KS Tumor Assessment, Photographic Record		X ^d	X ^g		X ^{h,r}				X	X ^r	X ^x
Concomitant Medication Review		X	X ^g	X ^h	X ^h						
Assess Adherence to Antiretroviral Therapy	X ^u	X	X ^g	X ^h	X ^h				X		
Review of current and prior anti- HIV therapy (if HIV positive), prior immune based therapy and prior anti-tumor therapy		X	X ^g		X ^h				X		
FAHI+KS Quality of life questionnaire (see Appendix XII)		X ^k	X ^k				X ^m (Cycle 4 only)			X	
KS staging		X ^b							X	X	
CBC with Differential, Serum Chemistries ^l		X	X ^h	X ^h	X ^h		X ^h		X	X	
CD4 and CD8 Count (T Cell Subsets), and HIV-1 plasma		X ^b	X ^l		X ^h (Cycle 4, 7,				X		

	Eligibility	Screening/ Baseline	Cycle 1 Day 1	Cycle 1 Day 15	Cycles 2 – 12				Treatment Discont.	Post Treatment Eval.	Follow Up Visits
					Day 1		Day 15				
RNA, if HIV-positive					10 only)						
HHV-8 Viral Loads (see Appendix III)		X ^{k, y}	X ^{k, y} (predose)		X ^{aa} (Cycle 4, 7, 10 only)				X		
Serum or Urine HCG Pregnancy Test ^c		X ^c	X ^q								
Education and counseling guidance		X ^g									
Dispense sEphB4-HSA			X	X	X		X				

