Urinalysis		X	X ^w		X ^w				X		
Peripheral blood sEphB4-HSA levels (see Appendix II)			X (predose and immediately prior to end of infusion)	X (predose)	X ⁿ (predose)		X ⁿ (predose)				
Peripheral blood (for immune studies) (see Appendix III)		X ^{k, z}	X ^{k, z} (predose)	X	X ^o (predose)						
Peripheral blood (for PBMCs for Research) (see Appendix III)		X ^{k, y}	X ^{k, y} (predose)	X	X ^{aa} (Cycle 4, 7, 10 only)				X		
5-mm KS Biopsy (formalin-fixed), and 5-mm KS Biopsy (RNA later)		X ^k	X ^k (predose)	X ⁱ (after Day 15 dose)							
Chest X-ray ^f , CT Scan ^p		X ^b									
ACSR Donation (Screening or Day 1, optional with consent)		X ^j									

^a To be done any time prior to study enrollment

^b To be done ≤ 28 days prior to study enrollment

^c To be done ≤ 14 days prior to study enrollment

^d To be done ≤ 7 days prior to study enrollment

^e Pregnancy test to be done on females of childbearing potential

^f Participants with a positive CXR or minimal symptoms suggestive of pulmonary involvement of KS will have a CT thorax performed. CXR not required if a thoracic CT has been performed

^g Baseline assessments can be done on Day 1, or < 14 days prior to first dose of study drug

^h Labs may be done up to 7 days prior to days 1 and 15 of each cycle; interval history and physical exam must be done up to 7 days prior to study agent administration.

ⁱ To be done after Cycle 1, Day 15 dosing. Can be done any time after treatment on Cycle 1, Day 15 and before treatment of Cycle 2, Day 1

^j To be done at any time from time of study enrollment to Day 1, if the participant consents

^k To be completed within 14 days prior to Cycle 1, Day 1 of study drug. Baseline and Day 1 can be the same day

- ¹ Baseline and Day 1 can be the same (as long as done within 4 weeks of treatment)
- ^m To be administered anytime between Cycle 4, Day 15 and Cycle 5, Day 15
- ⁿ After Cycle 1, pre-dose blood for sEphB4-HSA trough levels only to be drawn days 1, 15 of Cycle 2.
- ^o Only on Day 1 of Cycles 2, 4, and 6; to be done before study treatment dosing. Given this will be a fresh blood sent at room temperature overnight, if the blood for immune studies cannot be collected on Monday-Wednesday (i.e., the dose is administered on Thursday or Friday), this blood work can be obtained the Monday AFTER the dose was given.
- ^p Only needed if symptomatic or specific findings on CXR
- ^q To be done within 24 hours of first dose of study drug

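### Females of childbearing potential must agree to ongoing pregnancy testing, but no test is scheduled after the one before the first dose, and none is required before a restart after complete response

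*Combined protocol and SAP*

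**What the plan says.** Section 3.1.9 requires a negative test within 14 days before enrollment and "again within 24 hours prior to starting Cycle 1 of sEphB4-HSA", and adds that "FCBP must also agree to ongoing pregnancy testing". Section 8.1.6 repeats both, with the tests placed "within 14 days prior to study enrollment and again within 24 hours of starting sEphB4-HSA". Appendix XI repeats the commitment but limits it to when testing is needed.

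The time points agree across the protocol:

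- Section 8.2.1.16: "Females of Childbearing Potential (FCBP) with regular, irregular or no menstruation must have a pregnancy test before study enrollment and on Day 1".
- Appendix I: the row "Serum or Urine HCG Pregnancy Test" is marked at Screening/Baseline and Cycle 1 Day 1 only. The footnote to the Day 1 mark reads "To be done within 24 hours of first dose of study drug".
- Appendix XI: before the start of drug and Day 1 of Cycle 1.
- Sections 8.2.2 (Cycles 2-12), 8.3 (discontinuation), 8.4 (post-treatment) and 8.5 (follow-up): no pregnancy test listed.

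Appendix XI adds one later provision. Testing and counselling are mandatory after a missed period, an abnormal pregnancy test or abnormal menstrual bleeding, and treatment stops during the evaluation. A positive test means immediate discontinuation.

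Abstinence or two simultaneous contraceptive methods are required "during receipt of sEphB4-HSA, and 12 weeks after discontinuation of sEphB4-HSA". Section 4.3 allows treatment to resume if KS progresses off treatment after a CR, within the 12-cycle maximum.

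**The concern.** Entry depends on agreeing to ongoing testing, yet a site following the schedule would run no further test unless something prompted it. The prompt in Appendix XI is largely menstrual. The protocol's own definition keeps a woman in the FCBP group if she "has had menses at any time in the preceding 24 consecutive months", and Section 8.2.1.16 names FCBP with irregular or no menstruation. For them, a missed period or abnormal bleeding may be hard to recognise.

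Section 2.3.4 says no reproductive or developmental toxicity studies have been done. Section 3.2.13 treats teratogenic or abortifacient effects as possible. Section 4.5 and Appendix XI stop treatment for pregnancy, but a stopping rule acts only once the pregnancy is detected. If contraception fails in a woman whose menses give no clear signal, dosing could continue through an unrecognised pregnancy. On the restart path, a woman who conceives after the contraception requirement has ended could be re-dosed without a test.

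**Working it through.** The plan states no figure for this point. The check compares the testing provisions with the dosing calendar.

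**Inputs.** Doses on Days 1 and 15 of 28-day cycles, at most 12 cycles (4.1, 4.3). Last scheduled test within 24 hours before dose 1 (3.1.9, Appendix I). Contraception for 12 weeks after discontinuation (3.1.9). Follow-up of responders for up to 1 year from Day 28 of the final cycle (8.5). Planned women: 3 in the ethnic panel and 4 in the racial panel of Table 12-A.

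**Doses without a fresh scheduled test.**
- Maximum doses: 12 × 2 = 24. Dose 1 is covered by the test before it, leaving 24 − 1 = 23.
- Cycle 12 Day 15 is study day 11 × 28 + 15 = 323, which is 323 − 1 = 322 days (46 weeks) after the first dose, if there are no delays.

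**What can start a later test.** Appendix XI has three triggers. With no test scheduled, an abnormal test cannot be the first signal. The other two, a missed period and abnormal bleeding, depend on a menstrual pattern the woman can recognise.

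**Restart after CR.** No restart provision (2.4, 4.1, 4.3, 10.1) mentions a pregnancy test or repeat screening. If a restart falls within the 1-year follow-up, the longest interval between the end of required contraception and the restart depends on where the 12 weeks begin:
- from Day 28 of the final cycle: 365 − 84 = 281 days, or 40.1 weeks;
- from the last dose on Day 15: 13 + 365 − 84 = 294 days, or 42.0 weeks.

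These are upper limits. An earlier restart gives a shorter interval or none.

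**Burden of testing every cycle.**
- Day 1 of Cycles 2-12 gives 11 tests per FCBP who completes 12 cycles. Restart cycles count within the 12, so a restart at a cycle's Day 1 adds none. With 0 to 4 FCBP, that is 0 to 44 tests in the trial.
- The documents give no false-positive rate. Assuming 0.1% to 1% per urine test, the chance of at least one false positive over 11 tests is 1 − 0.999^11 = 1.1% to 1 − 0.99^11 = 10.5% per FCBP. Over 44 tests, 44 × 0.001 = 0.04 to 44 × 0.01 = 0.44 are expected.

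**The case against.** The strongest reply is that the commitment has content. Sections 3.1.9, 8.1.6 and 8.2.1.16 all refer to Appendix XI, where ongoing testing applies when needed and a mandatory trigger appears in the same list. Read together, this is event-driven testing. That reading is fair, so a reader who infers that the protocol contradicts itself, or forbids testing after dose 1, goes too far. What remains is that the qualifier is absent from 3.1.9 and 8.1.6, and that the trigger is weakest in a group the protocol names.

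It can also be said that abnormal bleeding is a trigger, so absent or irregular menses might be read as meeting it. The documents do not show that the trigger fails in this group; the supportable claim is that it may not fire reliably.

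Other safeguards are real. Abstinence or dual contraception is the main one. Counselling, a Day 1 examination and symptom review each cycle, and testing at the clinician's discretion support it. After a CR, Section 8.5 provides visits every 3 months, and the Appendix XI trigger is not limited to dosing. Section 2.1 says CRs are rare, so restarts should be too. These points reduce the risk, but none requires a test before a dose.

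One might stretch the 24-hour test in 8.1.6 to cover any start of drug. It sits under baseline evaluations, however, and Appendix I ties it to the first dose.

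**Conclusion.** The point holds as a participant-safety gap in the schedule and is worth correcting. Up to 23 doses, over up to 322 days, follow with no fresh scheduled test, and no test is required before a restart after CR. The dose count assumes 12 full cycles; the 322 days also assume no delay.

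The number of women affected is small and unknown. Table 12-A plans 3 or 4 women; the documents do not say how many would be FCBP, have absent or irregular menses, or restart. The true number could be zero.

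Three stronger readings are not supported. It would be wrong to say that all 24 doses lack a test, since dose 1 is covered. It would be wrong to count every planned woman as exposed to an undetected pregnancy, since that also needs contraception to fail and the trigger and other checks to miss it. And the documents do not say the drug is teratogenic: Appendix XI calls this unknown. Efficacy, power and alpha are unaffected.

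**What to change.** Add a urine hCG for FCBP within 24 hours before the Day 1 dose of each of Cycles 2-12 and before the first dose of any restart after CR. Enter it in 8.2.2, 4.3, Appendix I and Appendix XI. Align the wording on ongoing testing in 3.1.9, 8.1.6 and Appendix XI, and keep the existing trigger as an addition.

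Urine is already collected on Day 1 of each cycle for proteinuria (8.2.2.9). Section 8.2.2 allows laboratory work up to 7 days before Day 1, so a fresh sample at the dosing visit is needed when the urinalysis was done more than 24 hours earlier.

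Keep the Appendix XI rule that a positive test stops drug at once. If the sponsor wants to allow resumption after a negative serum confirmation, that bullet must be amended explicitly so that the two rules do not conflict. Confirmation should then be prompt: under Section 5.6 a delay of up to 48 hours keeps the same cycle, a longer one resets the schedule, and one over 28 days ends therapy.

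A test at discontinuation is optional, since it cannot prevent a dose in that course. The frequency is a judgement, as the documents set no standard. Testing only at Cycles 4, 7 and 10 would need 3 tests but leave 3 × 2 = 6 doses (84 days) between tests, against 2 doses (28 days) with testing every cycle.

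The cost is about 11 urine tests per FCBP who completes 12 cycles, with no new visit. The downside is an occasional short dose hold for a false positive, about a 1% to 11% chance per FCBP at the assumed rates, provided that resumption is allowed. If the bullet is left unamended, a false positive would end treatment, so the sponsor should decide this point deliberately.
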